### **Objective 3**

Within two weeks of each interview, the research assistant and the PI will meet to discuss the findings. Audio files will be transcribed by a research assistant. The PI and a research analyst will code and analyze the interviews using MAXQDA 2022 software or similar. Thematic analysis will be used to identify responses to our questions about the drivers, core facilitators, and barriers to intervention acceptability and success. Data will be coded by two independent coders to ensure that Cohen's Kappa is  $>85\%$ . One code map will be developed to categorize data: (1) to understand the factors related to the experience and occurrence of moral injury/ moral trauma

among HCW in the area, and (2) to understand what services or interventions may support HCW who are experiencing or at risk for moral injury/ moral trauma.

As the final surveys, anxiety and suicidality measures, will be assessed 10-11 months after the intervention, we are not expecting any impact of the intervention on these assessments. Because of this we will only conduct descriptive statistics, including summary measures across all four sites. We will compare the results of these measures by HCW gender, age, and site to look for trends in outcomes.

## 11. Ethical Considerations

The sites that participate in this proposal meet the requirements for the conduct of research using funds from the US Government. The protocol and consent forms will be reviewed and approved by the Vanderbilt University Medical Center IRB (FWA00005756, IRB00000475-7, IRB00002125) and the Institutional Committee of Health Bioethics-Zambézia, Mozambique (FWA00003139 IRB# IRB00002657). The proposed project is Non-Exempt Human Subjects Research.

All eligible health care staff will have the option to participate (or not) in the study without any implications on their job stability. The research activities will not alter in any way the treatment of HCW at the health facilities they work in, or the routine services that all patients are already expected to receive, nor will they adversely affect the rights and welfare of the study participants.

While we will obtain consent from all HCW who participate in the intervention and from those who complete any survey (HCW and PLHIV) or in-depth interview (HCW), we are requesting a waiver of consent for the population of adult PLHIV (who did not participate in a survey) whose clinical data will be extracted in a de-identified manner, due to:

- Data review will only involve a secondary analysis of routinely collected de-identified data and will not involve any interaction with human subjects.
- The data review involves no more than minimal risk to subjects.
- The research activities will not alter in any way the routine services that all patients are already expected to receive or adversely affect the rights and welfare of the subjects.
- Due to the high volume of patients and the inclusion of records for patients who might no longer be enrolled in care at these health facilities, the activity could not practicably be carried out without the waiver of consent.

### Participant confidentiality

All participants who are consented in the study will be assigned a study ID number. Only study members will have the codebook that links the identifiers. Identifying information associated with these ID codes, such as names, will be kept in a data file separate from the survey data and clinic records. All data will be managed in a way that meets VUMC IRB and Mozambique Bioethics standards for the protection of human subjects and to ensure confidentiality and the protection of sensitive health information.

### Consent Procedures

Review of study and participation information with potential subjects can be conducted in a group or individually but written informed consent must be obtained individually and in a confidential setting before any study procedure takes place (**Appendices 5-9**). Despite recruitment being done at the health facility, the study team will guarantee that interested individuals consent without any coercion, and that refusal of, interruption during, or withdrawal from the study will not result in negative consequences for receiving care (PLHIV patients) or for their professional work situation (Health Care Workers). A copy of the signed informed consent form will be offered to every participant. If an eligible individual is illiterate and/or unable to write or sign his/her name, he/she can provide a thumbprint in the presence of an independent literate witness. This witness must be present during the entire informed consent process and will sign the consent form as the witness only after the consenting participant has completed their thumbprint process. All written information, including the informed consent and other material to be used by participants and study staff will be translated from English into Portuguese and vice-versa, and will use vocabulary and language that are clearly understood. Although informed consent forms will be translated to Portuguese, verbal translation to main local languages (by study staff fluent in those languages) will be allowed to accommodate participants who do not speak Portuguese. Key phrases may be developed for main local languages to ensure correct verbal translation in the field by research assistants and to make the questions clearer to participants. Moreover, research assistants with fluency in Mozambique's major local languages will be hired to conduct surveys and interviews to increase inclusion of individuals who may not speak Portuguese fluently.

A participant may withdraw from the study at any time point. When a participant indicates to the study staff that they are withdrawing consent, this will be reported in the participant's source documents.

All participants will be informed that participation in the study is voluntary and refusal to participate will not affect their right to care and treatment at the health facility (PLHIV) or their employment and position at the health facility (HCW).

People living with HIV who are followed as part of routine care (n=~16,000) will not be formally recruited to participate in the study.

## **Evaluation of benefits and risks**

### **Adverse events**

*Risks to the subjects:* The level of risk associated with this research is expected to be minimal for all participants. Potential psychological discomfort may occur when administering the survey as many of the questions are personal and have to do with a stigmatized infectious disease and/or one's mental health and well-being, including suicidal ideation. Participants are able to decline to answer any question that they deem uncomfortable. If we identify a participant with suicidal ideation or severe depression, we will ensure they are referred to a psychologist for counseling to address their mental health concerns.

Participants (health care workers) who enroll in one of the two (or both) interventions will have the potential for inter-personal conflict as they brainstorm solutions to burnout or talk about stigmatizing experiences of patients.

**Adverse Experience/Event (AE):** We do not anticipate any adverse events as a result of this study, however, study participants will be provided with contact information (e.g., a telephone number) and instructed to contact study clinicians to report any serious AEs they experience.

**Protection against risks:** The study protocol and training manuals will include strict guidelines for conducting the survey and recording the data in a confidential manner. All study staff will receive formal responsible conduct of research training per NIMH, VUMC, C-Saúde, and Mozambican MOH guidelines. Participants may withdraw from the study or decline to participate in any study activity for any reason at any time, and they will be informed of this at the recruitment and enrollment stage prior to study participation.

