#### Wellness and Resilience Intervention

Health care workers working at sites randomized to resilience training or the combination anti-stigma and resilience training will receive a group-based Mindfulness-based Wellness and Resilience (MBWR) intervention. The training course will occur every other week and consist of 4 sessions of 60-120 minutes each. The day and time of the intervention session will be determined by health facility staff to facilitate attendance. We will focus on common challenges encountered in the health facility, as well as coping strategies, and future goals to improve provider well-being.

The team selected a group-based, mindfulness-based wellness and resilience (MBWR) intervention. MBWR is designed to be a brief, cost-effective, evidence-based, and replicable intervention to enhance resilience and self-compassion among teams providing primary health care services. The training is based on an established Mindful Practice curriculum^63 and Mindfulness-Based Stress Reduction curriculum. This intervention was selected because it focuses on developing resilience and self-care at the team level (which is how HIV care and treatment is delivered) and because the training can be conducted by a trained Bachelor-level psychologist. The original training course consists of weekly sessions of 60-120 minutes each over 6-10 weeks. Our team has adapted the curriculum to include common challenges encountered in these health facilities, facility-level strategies that can empower health care workers to improve conditions, individual coping strategies, and future goals to improve HCW well-being (see **Table 2**).

**Table 2:** Adapted Wellness and Resilience Training Topics

Focus of Resilience Training Sessions	Intended Learning outcomes
1) Burnout and its consequences and ways to respond/ when to seek care	
 
Factors that may lead to the feeling/ experience of burnout;
 
Understand the signs and symptoms of burn-out and the consequences of not-identified burn-out among health care workers;
 
Getting skills to help colleagues in identifying symptoms;
 
Know how to recognize burnout and where to refer to if experiencing symptoms;
 
Interactive component: share ways that burnout impacts either yourself or colleagues who you work with.
 

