2) Self-care and ways to cope with work-related stressors & Teamwork and social support	
 
Getting coping strategies skills to overcome some work-related stressors;
 
When and how to seek care from others/ a professional;
 
Interactive component: practice examples of self-care (e.g., meditation, breathing exercises, etc.).
 
Understand the importance of teamwork/ social support in the prevention of work-related stress and in the provision of better patient care;
 
Interactive component: brainstorming ideas for social support/group activities that could be supported by and/or at the workplace.
 

3) Communicating and managing interpersonal relationships with others (ex. colleagues, patients, etc.), conflict handling in the work setting	
 
How to better communicate with others in the workplace and resolve work setting conflicts;
 
Ways to advocate for self and communicate expectations among team members;
 
Interactive component: what options for improving communication and/or interacting with others might work at your facility; role play with other participants to practice navigating difficult conversations (e.g., in pairs, could share with larger group).
 

4) Finding better balance between life and work activities/responsibilities	
 
Describe responsibilities that one may juggle between life and work;
 
Discuss ways to build healthier balance in work and life activities/priorities;
 
Interactive component: pairs or small group discussions for personal experiences of 'juggling' responsibilities, brainstorming ways to have better balance.
 

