#### Anti-Stigma Intervention

Health care workers working at sites randomized to the anti-stigma only or the combination anti-stigma and resilience arm will receive anti-stigma training sessions to address issues with multiple stigmas that may be impacting their ability to provide quality care for PLHIV in Mozambique. The training will occur once every other week, for at least 4 sessions of 60-120 minutes each. The day and time of the intervention session will be determined by health facility staff to facilitate attendance.

Study personnel will work with health care workers at study sites to combine and adapt the most applicable components from three evidence-based anti-stigma interventions. These interventions were selected because: i) they were developed in low and middle income settings (and parts of one intervention have been tested in Mozambique through International Association of Providers of AIDS Care [IAPAC] modules), ii) their focus is on identifying HIV-related and other intersecting stigmas, the impact stigma has on patients, the impact stigmatized beliefs have on health care providers, and iii) they propose ways to create a stigma-free environment in the health setting (see **Table 3**).

**Table 3:** Adapted Anti-Stigma Sessions

Title of exercise/session	Intended learning outcomes
1. Naming stigma through pictures/defining stigma; describing the different types of stigma; consequences of stigma	
 
Participants discuss what similar stigma takes place in different contexts and start to share stories of what they have personally witnessed.
 
Recognition of how personal attitudes and beliefs influence stigmatizing behavior.
 
Helps participants to recognize the causes of stigma and how the resulting effects are manifested.
 
Interactive component: brainstorming as a group the types of and expressions of stigma in the workplace.
 

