## **Procedures for Health Care Workers**

### Survey Data Collection (Objectives 1 and 3)

All health care workers who agree to enroll in the study will be asked to complete study questionnaires i) at baseline, ii) within 1 month after last session (or 6 months after enrollment in the control site), and iii) approximately 10-11 months after enrollment. Sociodemographic data will be collected within the baseline survey. We will measure HCW attitudes (n=100) towards their patients (stigma), as well as factors associated with well-being, including resilience, burnout, depersonalization, moral injury, depression (endline only), anxiety (endline only), and the Suicide Screening (endline only) (see **Table 4**; see **Appendix 1** for each measure). Details on the co-primary outcomes are noted below.

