#### Personal burnout

1. How often do you feel tired?
2. How often are you physically exhausted?
3. How often are you emotionally exhausted?
4. How often do you think: "I can't take it anymore"?
5. How often do you feel worn out?
6. How often do you feel weak and susceptible/vulnerable to illness?

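### The protocol foresees inter-personal conflict in the trainings, but its only stated event-reporting instruction asks participants for serious AEs

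*Combined protocol and SAP*

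**What the plan says.** Section 11, under Adverse events, rates the risk to all participants as minimal. It then adds a risk specific to the trainings: staff enrolled in one or both "will have the potential for inter-personal conflict as they brainstorm solutions to burnout or talk about stigmatizing experiences of patients". The next paragraph says no adverse events are anticipated. It also says participants will receive contact details and be "instructed to contact study clinicians to report any serious AEs they experience". The visible text defines neither an adverse event nor a serious one.

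The exercises make the foreseen risk concrete. In Table 2, resilience session 1 asks staff to "share ways that burnout impacts either yourself or colleagues who you work with", and session 3 includes "role play with other participants to practice navigating difficult conversations". Participants are permanent staff of the same facility (Section 7b), so they go on working together afterwards.

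The amount of training is stated for each course. For resilience: "The training course will occur every other week and consist of 4 sessions of 60-120 minutes each". For anti-stigma: "The training will occur once every other week, for at least 4 sessions of 60-120 minutes each".

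**The concern.** The protocol names a harm and then sets a reporting threshold that this harm would usually not reach. A quarrel that began in a session and soured a working relationship, or distress after being discussed by colleagues, is unlikely to be seen as a serious AE. A participant who follows the instruction exactly would have no reason to call.

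Two things are at stake. The first is modest participant protection, because someone upset by a session is not told that the study team wants to know. The second is the harm record. Section 12 says the data will inform the design of a fully powered trial. An empty list of events from this pilot could be taken as reassurance, although the foreseen harm was not asked for.

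**Working it through.** The protocol gives no figure to reproduce. The check is whether any other visible text supplies a reporting route for non-serious, session-linked events.

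- **Psychologist referral (Section 11).** Triggered by suicidal ideation or severe depression. Conflict is not covered.
- **Protection against risks (Section 11).** Covers survey conduct, confidentiality, staff training and the right to decline or withdraw. It says nothing on recording session events.
- **Withdrawal (Section 11, Consent Procedures).** Noted in source documents. No reason is requested, so a withdrawal caused by a session would not be identified.
- **Facilitators (Section 8, Intervention designs; Table 2).** Facilitators support the practical work, and resilience session 3 covers handling conflict at work. This is mitigation. No session record is described.
- **Burnout and depersonalization surveys (Section 8; Appendix 1).** Repeated after the sessions and analysed as changes from baseline. Items such as "How often are you emotionally exhausted" track general distress. They do not tie it to a session or ask about conflict with colleagues.
- **Depression and anxiety screens (Appendix 1; Section 10, Objective 3).** These ask how far any reported problems hinder getting on with others, at months 10-11. The Timeline puts the sessions in months 1-4, and the items do not refer to them.
- **Objective 1 interviews (Section 8; Appendix 3).** Question 4 asks how the program fell short or failed, and question 5 asks about changed interaction with colleagues. Both could draw out conflict. The coding in Section 10 concerns acceptability, success and sustainability; no harm code is described.
- **Objective 3 interviews (Appendix 4).** A probe on work atmosphere could touch on conflict, but the coding is about moral injury and support services.

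Several sources may therefore surface such events, but none is a stated route for reporting them.

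For scale only, the planned exposure, assuming one group per site:

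- Sessions: resilience-only 4; anti-stigma-only at least 4; combined 4 + 4 = at least 8. Total 4 + 4 + 8 = at least 16. If the combined site merges the courses, 4 + 4 + 4 = at least 12.
- Group contact at 60-120 minutes: 16 sessions give 16-32 hours; 12 sessions give 12-24 hours.
- Person-sessions at the plan's maximum of 25 staff per site and full attendance: 25 × 16 = 400, or 25 × 12 = 300.
- Interview reach: 3 × 25 = 75 intervention staff at most and up to 40 interviews, so 40 / 75 = 53% at that enrolment.

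These figures show how much training and interviewing is planned. They do not measure missed events.

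**The case against.** The strongest reply has four parts.

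**Unseen text.** The consent forms for health care workers and the training manuals are natural places for a fuller instruction or a facilitator log, and neither is visible. This stands as a limit: the point concerns the rule stated in the protocol, and a reader should not infer that the study has no other route. It does not remove the restriction to serious events in Section 11.

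**The rule addresses participants only.** It does not stop facilitators from recording what they see. That is correct, but nothing visible asks them to.

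**Handling and capture are better than the AE paragraph suggests.** Facilitators are present, one session teaches conflict handling, and question 4 of the Objective 1 guide prompts directly for failures. Conflict could be coded as a social barrier to acceptability. Section 10 also announces three code maps and lists two, so the coding is not fully described. All of this stands. A reader might infer that the trial is blind to this harm; the documents do not support that. They support only that such events could surface without a stated commitment to report them.

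**Some difficult exchange is intended content.** This also stands, so any wider rule needs a line between useful friction and harm.

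A reader might also take the 300-400 person-sessions as the size of the defect. They are exposure under maximum enrolment and full attendance. With no conflict rate in the documents, they cannot be turned into a number of missed events.

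**Conclusion.** The mismatch within Section 11 is real and minor. The protocol foresees inter-personal conflict in the trainings. Its only stated event-reporting instruction asks for serious AEs, so non-serious conflict or distress linked to a session would not be reported under the rule as written. Facilitator support, the conflict-handling session and the open interview prompts mitigate this but are not stated reporting routes.

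The conclusion rests on the visible text alone and on such conflict usually falling short of a serious AE, a term the protocol does not define. Conflict severe enough to count as one would still be reportable. Neither co-primary outcome, no patient outcome and no planned test is affected. The gain from a change is a modest improvement in participant safety and in the harm record.

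**What to change.** In Section 11 (Adverse events), replace the words 'any serious AEs' with: *any serious AE, and any conflict or distress linked to a session that they found harmful or that continued after it*. The qualifier leaves out the difficult exchanges that the exercises intend. List these reports descriptively by site, or as a three-site total if site counts could identify someone.

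The sessions may already be over: Appendix 4 quotes survey results, although its moral injury figure comes from a scale given only at baseline and so does not settle the matter. If they are over, tag mentions of session-linked conflict or distress in the Objective 1 interview coding (Section 10) and describe them as a theme. They should not be presented as a rate, because interviewees are chosen purposively (Section 7e). Section 10 keeps electronic transcripts for 5 years, so this remains possible.

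The cost is a few words in one paragraph and a short descriptive listing, or one extra code on interviews already planned. No new visits, staff or instruments are needed. A few minor events will be logged. Reporting stays participant-initiated, so the change does not yield an incidence of conflict, and an empty record would still not show absence of harm.

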### **Benefits**

People living with HIV could benefit from this study if health care workers who receive the wellness and anti-stigma intervention provide more compassionate health services to PLHIV.

HCW in this study could potentially benefit from their additional resilience and anti-stigma training, which could help improve their own well-being.

## **12. Limitations**

Our pilot cluster randomized controlled trial has the strength of being implemented in the most common type of health facility- a district clinic. We have designed our study in this way to be able to identify which intervention (or combination of interventions) is the most successful in both changing health care worker psychosocial characteristics and patient outcomes. Both outcomes will inform future iterations of this program. A cluster randomized controlled trial with only four sites is inherently limited, but we are using this data to inform the design of a fully powered future trial.

